#### **6.1.7 Missed Doses**

If participants miss a scheduled dose, that dose should be skipped. Regular dosing should resume with the next scheduled dose. Participants should not take any extra doses to make up for missed doses.

---

#### **6.1.8 Interruption of Study Treatment**

Any participant with an actual or anticipated interruption of study treatment for a period of  $\geq 28$  consecutive days will be reported by telephone to the study's medical monitor or designee to discuss the circumstances of the case. Once the participant restarts study treatment, the dose may be re-titrated as described in Section 6.1.6. A pre-restart visit is required, as described in Section 5.3.5.

---

#### **6.1.9 Precautionary Measures**

Drug-induced liver injury (DILI) has been observed with pirfenidone. In the postmarketing period, non-serious and serious cases of DILI, including severe liver injury with fatal outcome, have been reported. Patients treated with pirfenidone had a higher incidence of ALT and/or AST elevations of  $\geq 3x$  ULN (3.7%) compared with placebo patients (0.8%). Increases in ALT and AST  $\geq 3x$  ULN were reversible with dose modification or treatment discontinuation.

Measure liver function promptly in patients who report symptoms that may indicate liver injury, including fatigue, anorexia, right upper abdominal discomfort, dark urine, or jaundice. Dosage modification or interruption may be necessary for liver enzyme elevations. See Table 1.

Pirfenidone is causally associated with DILI, mainly in the form of transient liver enzyme elevations of no clinical relevance. However, clinical manifestations of DILI including cases with fatal outcome – possibly caused by idiosyncratic reactions to pirfenidone – have been reported in rare instances.

Exposure to sunlight (including sunlamps and tanning beds) should be avoided or minimized during study treatment due to the possibility of photosensitivity reactions or rash. Participants should be instructed to use sunscreens that have a sun protection factor (SPF) of 50 or higher as well as protection against ultraviolet A (UV-A) radiation, and also to wear clothing that protects against sun exposure and avoid concomitant medications known to cause photosensitivity reactions, if possible.

All doses of study treatment are to be taken with food to reduce the likelihood of gastrointestinal symptoms. The dose titration period of 21 days at the initiation of study treatment is designed to maximize tolerability.

## 6.2 STUDY AGENT ACCOUNTABILITY PROCEDURES

The monitoring of the inventory of study treatment supplies may be delegated to the responsible pharmacist; however, the Investigator is ultimately responsible for monitoring of study treatment inventory. Study treatment may not be used for any purpose other than that described in the protocol. All study treatment must be stored in a secure place with access restricted to authorized personnel.

Participants should return all used and unused bottles of study treatment at every visit. After drug accountability has been assessed and drug return has been authorized by the clinical monitor, sites may return all used and unused study treatment bottles to the distribution center or destroyed in accordance with site-specific standard operating procedures.

All bottles of study treatment will be recorded in a Drug Accountability Log. The Investigator or designee will account for all study treatment received at the site, dispensed to the participants, returned by the participants, not used, and destroyed. All documentation of study treatment shipments must be retained.

## 7 STUDY PROCEDURES AND SCHEDULE

### 7.1 STUDY PROCEDURES/EVALUATIONS

Informed consent must be obtained prior to Screening and before any study-mandated procedures take place. Study procedures are defined as laboratory tests, spirometry, lung volumes, DLCO (carbon monoxide transfer capacity), ECG, HRCT scan, directed history, physical examination, vital signs, height, weight, and any changes to existing treatment regimens. During the study, procedures and observations will be monitored to confirm that study requirements are being followed as outlined in Appendix A. If any study procedure related to PFTs and imaging is deemed not acceptable for quality issues, the procedure should be repeated.

---

### **7.1.1 Laboratory Assessments**

#### Routine Clinical Laboratory Tests

The following research related assessments will be performed locally at each clinical site, according to Appendix A, as summarized below:

- Hematology (complete blood count with platelet count and automated differential)
- Serum chemistry profile (albumin, alkaline phosphatase, ALT/SGPT, AST/SGOT, total bilirubin, calcium, creatinine, glomerular filtration rate (eGFR), gamma-glutamyl transferase [GGT], glucose, potassium, sodium, BUN, uric acid and amylase)
- Blood Pregnancy test for women of childbearing capacity
- Serology assessments include Erythrocyte Sedimentation Rate (ESR), Rheumatoid Factor (RF), C-Reactive Protein (CRP), and Cyclic Citrullinated Peptide (CCP)

It is the investigator's responsibility to perform clinical laboratory assessments more frequently, if clinically indicated.

#### Biomarkers in Blood

Research laboratory studies will be conducted at Baylor College of Medicine. Blood samples obtained for research studies will be shipped to Baylor College of Medicine. Biomarker samples include Serum, Plasma, and RNA. These samples will be collected according to Appendix A. Samples will be labeled with a unique study code and stored at the Biorepository at Baylor College of Medicine for future research.

Certain biomarkers may be differentially expressed in RA-ILD and may change as a result of pirfenidone treatment (e.g., possibly cytokines, chemokines, microRNA expression, and other cellular and molecular markers of fibrosis). The blood samples that are being obtained for this study may help identify these biomarkers and may be used to assess their response to pirfenidone therapy.

#### Genetic Polymorphisms (Assessed at Participating Sites)

Genetic polymorphisms have been demonstrated to alter the development and clinical course of a number of different diseases. The purpose of assessing genetic polymorphisms in this study is to understand their potential role in the pathogenesis of RA-ILD and in clinical outcomes.

The assessment of genetic polymorphisms will be conducted at all institutions that agree to offer this assessment. Participant participation for this assessment is voluntary and declining participation will in no way influence eligibility for this study. Participants agreeing to participate will opt in on the informed consent form. Blood samples for genetic research include DNA PAXgene samples. These samples will be collected according to Appendix A. Samples will be labeled with a unique study code and stored at the Biorepository at Baylor College of Medicine for future research.

## 7.1.2 Clinical Assessments

### HRCT Scans

HRCT scans obtained before the Screening period as part of the standard of care for a participant may be used to confirm eligibility, provided they meet all of the image acquisition and quality criteria required by the central expert readers and were obtained within 3 months before the start of the Screening Period (see Appendix A). All HRCT digital images are to be stored on a dedicated disk or tape at each study center. The images will be transferred electronically to the vendor tasked with interpretation and archiving of the images.

To assess for eligibility, HRCT scans will be evaluated for:

- a. presence and extent (to nearest 10%) of reticular abnormality, ground glass, honeycombing, mosaic attenuation, nodules, consolidation, emphysema, overall extent of fibrosis.
- b. Semi-quantitative estimates of extent by central reader.
- c. Presence of traction bronchiectasis, non-traction bronchiectasis (common in RA), subpleural sparing, centrilobular nodularity, tree in bud, crazy paving, pleural thickening and/or effusion.
- d. Distribution of abnormalities:
  - i. Subpleural, peribronchovascular predominance or diffuse in axial plane
  - ii. Upper lung, mid lung, lower lung predominance or diffuse in craniocaudal plane
- e. Radiologic pattern of abnormality: UIP, NSIP, indeterminate, mixed (Lynch DA, Godwin JD, Safrin S, Starko KM, Hormel P, Brown KK, et al. High-resolution computed tomography in idiopathic pulmonary fibrosis: diagnosis and prognosis. *Am J Respir Crit Care Med.* 2005 Aug 15;172(4):488-93.)

The HRCT scans will be reviewed by a central reader who is a radiologist with expertise in RA-ILD prior to randomization. An adjudication committee will be available to assist with difficult cases. Data regarding the HRCT interpretation will be entered electronically into the Data Coordinating Center (DCC) database and incorporated into the clinical database.

### Surgical lung biopsy

Surgical lung biopsy (SLB) or transbronchial biopsy, if performed, may be obtained up to 4 years before randomization. Data regarding the pathology findings will be entered directly into the electronic case report form (eCRF). Participant eligibility will be communicated to the study site by the investigators' designated vendor.

### Spirometry and DLCO/TLCO Measurements

All equipment, procedures, and personnel qualifications for the assessment of lung function are based on the recommendations of the American Thoracic Society (ATS 2005) and will be performed and interpreted in accordance with published guidelines (Crapo 1994):

Spirometry measurements will include FVC and FEV1 before and 10-15 minutes after administration of a bronchodilator [albuterol (or salbutamol) from a metered dose inhaler] at screening. The remainder of the spirometric studies will be performed without bronchodilator administration.

Lung volume measurements will be performed by body plethysmography and should be performed before or at least 30 min after the last bronchodilator puff.

DLCO/TLCO will be measured by determining the diffusing capacity of the lung for carbon monoxide.

DLCO/TLCO measurement should be performed before or at least 30 min after the last bronchodilator puff.

All FVC data collected throughout the study will be evaluated by a central reader blinded to treatment assignment. Data for FVC and FEV1, will be entered electronically into the vendor's database and incorporated into the clinical database. DLCO/TLCO will be entered into the clinical database by the site.

### Patient Reported Outcomes

A spectrum of validated questionnaires will be used to assess patient related outcomes that include disease specific, overall health, and their perspectives on symptoms, performance and quality of life. These questionnaires have been endorsed by the OMERACT as the essential core set that should be included in the trials of Connective Tissue Disease-Interstitial Lung Disease. Domains that are advocated include: 1. Health Related Quality of Life (HRQOL), 2. Dyspnea, 3. Cough, 4. Patient Global Assessment, and 5. Function.

a) HRQOL instrument: St. George's Respiratory Questionnaire (SGRQ): SGRQ, a respiratory disease-specific HRQOL instrument that was originally developed for use in chronic obstructive pulmonary disease, has more recently been used in interstitial lung disease.

b) Dyspnea: Dyspnea 12 questionnaire (D-12): The D-12 is a unidimensional questionnaire with 12 items that provides a global score of breathlessness severity that incorporates both "physical" and "affective" aspects. The score is calculated using simple summation of the responses for each item (0 "mild" to 3 "severe"); thus, the total score ranges from 0 to 36, with 36 representing maximal severity. It has been validated in Connective Tissue Disease-Interstitial Lung Disease.

c) Cough: Leicester Cough Questionnaire (LCQ): This self-administered 19-item questionnaire for the quantitative assessment of symptoms of cough frequency and severity.

d) Patient global assessment (DAS28 Section B Global Health Questionnaire): DAS28 Section B is a single item visual analog scale that assesses global severity of the patient due to their disease.

e) Function: Health assessment questionnaire (HAQ20): It is a 20-item questionnaire to assess daily functional disability. It is validated in RA and is universally used in clinical trials of RA.

f) RAPID3: The Routine Assessment of Patient Index Data 3 (RAPID3) is a questionnaire that has been validated for rheumatoid arthritis to assess patient physical function, pain, and global assessment.

#### Physical Exam and Vital Signs

A complete physical examination should be performed on the day of the visit, including all body systems pertinent to the participant. If clinically significant abnormalities are observed before Day 1, they should be reported in the participant's medical history. If clinically significant abnormalities are observed after Day 1, the investigator should decide if they are new adverse events. Vital signs for this study protocol include heart rate and blood pressure.

#### Disease Activity Score (DAS28)

The DAS28 will be scored by an investigator based on clinical examination including swollen and tender joint counts performed by the investigators and lab results (ESR and CRP), as well as patient global assessment score.

#### Physician Global Assessment

Physician Global Assessment questionnaire asks physicians to rate the patient's overall health in the last week.

#### Vital Status Assessments

Vital status must be assessed at protocol-specified time points until the Follow-Up Visit, even if the participant cannot physically be present for the visit. Participants who chose to withdraw from study procedures early will be followed for vital status until Visit 12/End of Study Phone Call whenever possible.

Vital status procedures are as follows:

1. In the case of lung transplant, the date of the transplant, details of the transplant, dates of hospitalization, and the current vital status will be obtained
2. In the case of participant death, the date, details, and cause of death will be obtained if possible
3. If a participant is lost to follow-up, vital status will be ascertained through the use of Death Registries, where approved and available (see 5.3.7)

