### 2.1.3.6 InterMune Pooled Phase 3 Safety Data

Safety results from the pooled PIPF-004 and PIPF-006 pirfenidone 2403 mg/d study population were similar to those in previous studies. Common treatment-emergent adverse events (AE) that occurred more frequently in the pirfenidone group than the placebo group included gastrointestinal disorders (nausea, diarrhea, dyspepsia, vomiting, and stomach discomfort), skin disorders (rash and photosensitivity reaction), anorexia, decreased appetite, fatigue, and dizziness. Although more pirfenidone 2403 mg/d than placebo patients had at least 1 dose reduction for at least 1 day, dose reductions implemented in accordance with the protocol-specified guidelines tended to be short-lived and were typically related to transient gastrointestinal events or skin disorders. The rate of treatment discontinuation due to an AE in the pirfenidone 2403 mg/d group was only 6% higher than in the placebo group. Mild or moderate serum transaminase elevations (serum ALT or AST  $>3 \times$  upper limit of normal [ULN]) occurred more frequently in patients treated with pirfenidone 2403 mg/d than placebo, but they were most often effectively managed with dose modification and not associated with untoward clinical consequences. More extreme elevations in serum ALT or AST ( $>10 \times$  ULN) were rare in both treatment groups, and no instances of liver function abnormality meeting the criteria for Hy's law occurred.

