## 4.2 STUDY ENDPOINTS

### 4.2.1 Primary Endpoint

The primary outcome variable of this study will be the incidence of the composite endpoint of decline from baseline in percent predicted FVC of 10% or greater or death during the study treatment period.

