**Visit 12/End of Study Phone Call (28 days after last dose of study drug, ± 1 week)**

1. Review of AEs/SAEs
2. Vital Status Assessment

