#### 8.3.2 Serious Adverse Event Reporting

All SAEs will be graded for severity and relevance to study agents as detailed above, and recorded with start dates occurring any time after informed consent is obtained until 28 days after the last day of study participation. At each study visit, the investigator will inquire about the occurrence of SAEs since the last visit and study participants and their significant others will be asked in advance to

notify the study investigators immediately regarding any hospitalization, serious change in their health or in the event of a death. Events will be followed for outcome information until resolution or stabilization.

Regardless of whether the SAE is deemed related to use of the study agents, the data for the SAE must be reported with the appropriate information by the study investigators or their designee within 24 hours of learning of the event. In addition, new follow-up data must be reported within 24 hours of receipt. The medical monitor or designee may be contacted at any time for immediate discussion regarding such an event.

Investigators must report all SAEs to their governing IRB/IEC, as required by local regulations and guidelines.

Deaths in patients who withdraw from study procedures early and continue with Vital Status Assessments will not be considered SAEs if the death occurs more than 28 days after last dose of study treatment.

A record of all SAEs, by study subject, will be databased by the DCC.

---

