### 10.2 SAMPLE SIZE AND POWER CONSIDERATIONS

#### 10.2.1 Primary endpoint:

Table 1A shows sample size calculations and Table 1B shows power that will be achieved for some feasible scenarios with the selected sample size. Hypothesized estimates of treatment response in both placebo and pirfenidone arms were derived from the report of the Pirfenidone trial in IPF (King, et al., 2014.) If participants with RA-ILD are similar, then the proposed sample size of 254 participants (127 per group) will provide 85% power to demonstrate the treatment difference in terms of the combined primary endpoint reached by week 52, defined as either death or a decline from baseline of  $\geq 10$  percentage points in the percent predicted FVC. It is possible that participants with RA-ILD will have fewer endpoints than participants with IPF. Table 1B and Figure 1 show that power will remain sufficient for several scenarios where participants have fewer endpoints, and showing the robustness of the power to slight deviations from the hypothesized treatment estimates with the selected sample size. **The number of participants randomized will be 270** because of possible loss of data due to participants dropping out before week 52 or other reasons.

PASS version 13 was used for power calculations (PASS 13 Power Analysis and Sample Size Software, 2014, NCSS, LLC. Kaysville, Utah, USA, [ncss.com/software/pass](http://ncss.com/software/pass)).

Table 1: Power analysis for combined major endpoint reached by week 52, defined as either death or a decline from baseline of  $\geq 10$  percentage points in the percent predicted FVC.

A. Sample Size Calculation, 5% alpha, 2-sided

Power	Sample Size Each Arm	Total Sample Size	Proportion Placebo	Proportion Pirfenidone	Difference
0.80	141	282	0.30	0.16	0.14
0.85	161	322	0.30	0.16	0.14
0.90	188	376	0.30	0.16	0.14
0.80	111	222	0.32	0.16	0.16
0.85	127	254*	0.32	0.16	0.16
0.90	148	296	0.32	0.16	0.16

[figure not shown]
\* The anticipated total number of participants is 254.

B. Possible Scenarios with fewer endpoints, 127 on each arm (254 total), 5% alpha, 2 sided.

Proportion Placebo	Proportion Pirfenidone	Difference	Power
0.24	0.08	0.16	0.94
0.24	0.10	0.14	0.85
0.24	0.11	0.13	0.78
0.26	0.08	0.18	0.97
0.26	0.10	0.16	0.92
0.26	0.12	0.14	0.82
0.28	0.12	0.16	0.89
0.28	0.13	0.15	0.85
0.28	0.14	0.14	0.79
0.29	0.13	0.16	0.88
0.29	0.14	0.15	0.83
0.29	0.15	0.14	0.77
0.30	0.14	0.16	0.87
0.30	0.15	0.15	0.82

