### 10.4.2 Efficacy Analyses

Demographic data and baseline characteristics will be summarized by treatment arm. The primary analysis population will be the ITT population. The main analysis framework will be logistic regression to assess treatment differences in the primary outcome, defined as either death or a decline from baseline of  $\geq 10$  percentage points in percent predicted FVC, reached by week 52. Baseline for spirometry is defined as the screening visit with the assumption that values are the same at randomization. Baseline for other variables is defined as the randomization visit for variables collected at randomization, otherwise as the screening visit. The main predictor will be treatment arm, and covariates known to be related to the outcome and specified a priori (i.e., prior to database lock and unblinding), will be considered for inclusion. The stratification factor will be the site. Unadjusted and adjusted odds ratios, 95% confidence intervals and Wald test p-values will be reported. Similar analyses will be conducted with the listed secondary binary outcomes in Section 4.2.2. An additional secondary analysis of the primary endpoint will use the Per Protocol population.

Statistical analyses of the secondary outcomes that describe time-to-event will use Cox proportional hazards regressions using a similar approach as described above, reporting adjusted hazard ratios, 95% confidence intervals and p-values. Time will be measured from randomization until the event or until censoring. Kaplan-Meier plots will be generated, and proportionality of hazards will be assessed.

There are a number of secondary and exploratory outcome variables that are continuous, that will be calculated for each subject as follows: Each change from baseline to week 52 outcome will be calculated as the last value minus the baseline value. Each slope outcome will be derived from a linear regression of the values over the treatment period. The molecular expression outcomes will involve several genomic approaches to measure gene expression and protein levels with the purpose of identifying candidate biomarkers that differ according to treatment group.

All continuous secondary and exploratory outcomes will be summarized and inspected for unusual outliers and distributional characteristics, and the treatment arms will be compared statistically using the nonparametric Wilcoxon rank sum test.

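### For participants who withdraw from study procedures, vital status is scheduled only to 28 days after last dose, although the primary composite counts deaths to Week 52

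*Protocol*

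**What the plan says.** **Endpoint.** Protocol 4.2.1 makes the death component "death during the study treatment period", and Protocol 4.1 gives that period as 52 weeks. Protocol 10.4.2 defines the outcome as death or a decline of at least 10 "percentage points in percent predicted FVC, reached by week 52". Protocol 10.4.1 and the SAP (Analysis Populations) analyse everyone randomized. The SAP (Primary and Secondary Endpoints and Relevant Variables) codes death as yes or no while on study. It does not say when being on study ends for someone who has withdrawn.

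**Follow-up.** For early withdrawal from procedures, Protocol 7.1.2 states: "Participants who chose to withdraw from study procedures early will be followed for vital status until Visit 12/End of Study Phone Call whenever possible". The preceding sentence there requires vital status up to a Follow-Up Visit, which is not otherwise defined. Protocol 7.2.2 heads Visit 12 as the "End of Study Phone Call (28 days after last dose of study drug", with a one-week window. Protocol 4.1, Appendix A and the SAP (Study Assessments) use the same anchor.

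**Text that points elsewhere.** Protocol 8.3.2 says: "Deaths in patients who withdraw from study procedures early and continue with Vital Status Assessments will not be considered SAEs" when the death falls more than 28 days after last dose. This presumes that vital status is still being collected then. The SAP (General Study Design and Plan) puts the final call 28 days after Visit 11, though it mentions adverse events only. Protocol 5.3.4 ends vital status on written withdrawal of consent, yet still asks for the Visit 12 call where possible.

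**The concern.** The endpoint clock starts at randomization and runs to Week 52. For this group the vital-status clock stops four weeks after last dose. A participant who stops drug and leaves procedures at Week 8 has vital status planned to about Week 12 and nothing scheduled for the next 40 weeks.

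A death in that interval belongs in the composite, but no scheduled contact would find it. The SAP keeps every randomized participant in the primary analysis and gives no rule for unknown vital status at Week 52. The death would therefore default to a non-event unless the last FVC on study had already fallen enough to count. All-cause mortality, coded in the SAP by whether a death date is present, has the same weakness.

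Transpant recipients are a clear example. Protocol 5.3.4 and 7.2.2 take them off procedures and close with the same 28-day call. Transplant is not a primary event, but a later death before Week 52 is.

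**Working it through.** **1. The plan's own figure.** Protocol 10.2.1 states that the "proposed sample size of 254 participants (127 per group) will provide 85% power to demonstrate the treatment difference", at 0.32 versus 0.16 and two-sided 5%. The pooled-variance formula without continuity correction is

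n = [1.960·√(2·0.24·0.76) + 1.036·√(0.32·0.68 + 0.16·0.84)]² / 0.16² = (1.184 + 0.615)² / 0.0256 ≈ 126.4, so 127 per arm.

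The plan's figure is reproduced, with power 0.852 at 127 per arm. Nothing in this point changes it.

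**2. Who is affected.**

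| Participant | Source | Vital status planned to |
|---|---|---|
| Stops drug only | Protocol 4.1, 5.3.3, 7.2.2 (Unscheduled Visits) | Week 52, where possible |
| Withdraws from procedures without refusing vital status | Protocol 7.1.2 with 7.2.2 | 28 days after last dose |
| Lung transplant | Protocol 5.3.4, 7.2.2 | 28 days after last dose |
| Lost to follow-up | Protocol 5.3.7, 7.1.2 | Registry check, where approved and available |
| Withdraws consent in writing | Protocol 5.3.4 | Ceases |

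The gap lies in the second and third rows.

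**3. Length of the gap.** For last dose at Week t, the gap is max(0, 52 − (t + 4)) = max(0, 48 − t) weeks.

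| Last dose (week) | 8 | 13 | 26 | 39 | 48 |
|---|---|---|---|---|---|
| Unscheduled weeks | 40 | 35 | 22 | 9 | 0 |

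If last dose is uniform over 52 weeks, the mean gap is (48²/2)/52 = 22.2 weeks.

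**4. Expected missed deaths.** The documents give neither the share withdrawing from procedures nor their death rate. Assumed ranges are a share of 5–20% and an annual death risk of 5–20%, with constant hazard and uniform last dose. Expected missed deaths per arm = n × share × mean probability of death in the gap.

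| Share | Annual risk | Points of the composite | n = 127 | n = 61.5 (123/2) |
|---|---|---|---|---|
| 5% | 5% | 0.11 | 0.14 | 0.07 |
| 10% | 10% | 0.43 | 0.55 | 0.27 |
| 20% | 20% | 1.78 | 2.26 | 1.09 |

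The only loss allowance in the plan is implied: (270 − 254)/270 = 5.9%, which is near the low end of the assumed share.

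**5. Weight of one death.** At the planned rates, 123 participants give 61.5 × (0.32 + 0.16) = 29.5 primary events. One misclassified death is 1/29.5 = 3.4% of events, or 1/61.5 = 1.6 points in one arm.

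**6. Direction.** Suppose withdrawal from procedures were 6 points higher on pirfenidone (an assumption). With a placebo share of 5–10% and an annual risk of 5–20% in both arms, pirfenidone would lose 0.13 to 0.53 points more. That is 0.08 to 0.33 of a death at 61.5 per arm, against a design difference of 16 points. Now let mortality differ, using as a sensitivity value the pooled IPF hazard ratio of 0.52 reported in the protocol's account of the ASCEND trial. To a linear approximation, the sign reverses once 0.52 × (w + 6) < w, that is, once the placebo share w exceeds 3.12/0.48 = 6.5%. That ratio may not hold off drug. It shows only that the sign depends on inputs the documents do not supply.

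**The case against.** **The documents are not uniform on 28 days.** Protocol 8.3.2 foresees later deaths under continuing vital-status assessment, and one SAP section anchors the last call to Visit 11. This stands as evidence of intent. It does not close the gap, because neither text schedules a later vital-status contact.

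**Much is already covered.** Participants who stop drug only continue through Week 52, and those lost to follow-up get a registry check. Both points stand and narrow the affected group. The registry check is not written for someone who has withdrawn from procedures but can still be reached.

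**Not every gap death changes the endpoint.** The Early Termination Visit includes spirometry, and a sufficient decline there already counts. Deaths after written withdrawal of consent cannot be recovered by any follow-up rule. Both points stand, so the figures above are upper estimates of the composite events that the fix would recover.

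**A stronger reading is tempting.** The protocol reports from pooled IPF trials: "The rate of treatment discontinuation due to an AE in the pirfenidone 2403 mg/d group was only 6% higher than in the placebo group". A reader might infer that more deaths would be missed on pirfenidone and that the result would be biased in its favour. The documents do not support this. The figure concerns stopping drug for an adverse event, and those participants are followed through Week 52. No rate of withdrawal from procedures is given by arm, and the SAP (Missing Data) treats an excess of discontinuations or missing data in one arm only as a possibility.

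**Conclusion.** The point holds as a gap and an inconsistency in the follow-up rule. It is not a demonstrated bias. Followed literally, the protocol schedules no vital status between 28 days after last dose and Week 52 for participants who withdraw from procedures without refusing it, including transplant recipients. The SAP's death variable does not settle how they are scored.

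The expected loss is small: 0.07 to 1.1 deaths per arm at 123 randomized, given a withdrawal share and an annual death risk each assumed at 5–20%, uniform timing of last dose and constant hazard. The direction is unknown. The change is still worth making, because the loss falls on the primary endpoint, about 30 events are expected at the planned rates, and the remedy is cheap.

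**What to change.** - **Protocol 7.1.2:** follow vital status to the later of Week 52 after randomization and 28 days after last dose, for every randomized participant who has not refused it. Name the contact that closes it in place of the undefined Follow-Up Visit.
- **Protocol 5.3.7 and 7.1.2:** extend the registry check, where approved and available, to anyone without Week 52 vital status whose consent allows it.
- **SAP, primary endpoint variables:** define the death component as any death to Week 52 after randomization, regardless of treatment or procedure status.
- **Reconcile** Protocol 5.3.4, 7.1.2 and 8.3.2 with the SAP sections on General Study Design and Study Assessments, so that the final call has one anchor and written withdrawal of consent has one consequence.
- **Report** completeness of Week 52 vital status by arm.

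The cost is a few extra calls or lookups and some sentences in each document. Registry access depends on approval and availability, and it will vary across the four countries. Sample size, treatment and the primary test do not change.
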